## **7. Sample size calculation and Data Analysis Plan**

The primary endpoint of the study is drain duration (days). Mean postoperative duration of drain placement is 10 days. As per informal discussion with the plastic and breast surgeons, a minimum of 4 days in drain duration between the 2 arms will be considered clinically significant. We are hypothesizing that there will be minimum of 4 day difference in drain duration, in favour of Dermacell as this is a superiority trial. As such, we will require 50 patients total (25 per arm) to demonstrate a 4 day difference in drainage duration (14 vs 10) with a standard deviation of 5. Allowing for a 10% study drop out rate, we will require a total of 56 pts or 28 patients per arm. The Ottawa Hospital currently performs 100 immediate breast reconstructions per year with ADM. As such, the study duration would be expected to be 1 years. Data will be analysed at the end of the year.

November 24, 2016

The primary endpoint of the study is drain duration (days). We will compare mean postoperative duration of drain placement between both arms by calculating the post-randomization absolute mean difference in durations and its 95% confidence interval. We will also present the associated two-sample t-statistic. If data are not normally distributed, we will compare groups using a Mann-Whitney test. Our dichotomous secondary outcomes (episodes of seroma formation requiring aspiration, loss of implant, revisional surgery/ return to operating room, wound dehiscence or debridement, capsular contracture (as identified by the plastic surgeon) will be analyzed by calculating relative risk ratios and their 95% confidence intervals. Our continuous outcome (number of additional postoperative clinic visits with the plastic surgeon beyond the routine) will be analyzed using parametric (t-statistic) or non-parametric (Mann-Whitney) tests depending on distribution of occurrences. Patients having bilateral mastectomy will have each breast evaluated separately, as 2 entries the final results database. Both breasts of the same patient will receive the same randomization arm.

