Various ADMs are offered on the market and the costs vary widely despite very similar qualities. The two most commonly used ADM products in North America by far are Dermacell and Alloderm [2-4,32]. The difference between the two products include a) the level of sterility , with Dermacell being sterilized to  $10^{-9}$  while Alloderm is sterilized to  $10^{-6}$  and b) the consistency and thickness of the biologic material and c) a significant difference in cost (standard 6x16cm piece of Dermacell = \$2200 CAD and Alloderm = \$3600 CAD). For a typical patient, the difference in cost for the hospital is about \$1400. Supporters of Dermacell advocate for its lower cost and increased sterility; whether the difference in sterility translates into a clinical difference in infection rate is unclear (standard procedure is to sterilize to  $10^{-6}$  for operative devices) [32-36]. Supporters of Alloderm advocate based on its longer term data on safety and effectiveness (2-4,19,32] as it is the ADM that has been around the longest. Each product has shown to be safe and effective (32-26). As such there exists clinical equipoise. Currently, the selection of ADM is based on non-clinical idiosyncratic decision making factors, such as the hospital's previous relationship with the vendors and preference of the surgeon. Both products are equally available to Canadian hospitals and currently at the Ottawa Hospital the product used is dependent on surgeon preference.

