## 5. Outcomes

Primary outcome: Postoperative duration of drain placement (days)

Secondary outcomes: All outcomes are measured within 6 months of the initial surgery

- Episodes of seroma formation requiring aspiration

November 24, 2016

- Loss of implant
- Revisional surgery/ return to operating room
- Wound dehiscence or debridement
- Capsular contracture (as identified by the plastic surgeon)
- Number of additional postoperative clinic visits with the plastic surgeon (beyond the routine)
- Economic impact will be assessed based on calculation of total costs with each material used to include the material costs, duration of operative room use, clinic and inpatient hospital costs, surgical billing costs and anaesthesia costs

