## **6. Study Procedures**

All patients undergoing mastectomy for breast cancer or breast cancer prophylaxis are seen at the WBHC at the Ottawa Hospital. Patients eligible and consenting for immediate breast reconstruction with an implant will be introduced to the REACT-ADM study and a standardized verbal consent for randomization will be recorded in the clinic notes. The clinical research assistant (CRA) will be performing the randomization and will inform the surgeon on the day of surgery with regards to the randomization arm immediately before the surgery. Both Dermacell and AlloDerm will be readily available in the operating room for use in case of randomization into either arm.

The plastic surgeon will be informed of the randomization arm and will proceed with the surgery in the usual fashion, with standard, equivalent procedures used for both (aseptic technique, drainsplacement, oral antibiotics for 1 week postoperatively). The routine schedule of postoperative follow-up of these patients is as follows:

November 24, 2016

Breast Surgeon:

- 2 weeks
- 6 months

Plastic Surgeon:

- 1 weeks
- 2 weeks
- 6 months

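### Stratifying the randomisation by surgeon and adjusting the primary comparison for it would be a cheap gain in precision; the planned unadjusted analysis is valid but leaves any surgeon effect uncorrected

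*Combined protocol and SAP*

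**What the plan says.** The primary outcome (section 5) is the number of days the drain stays in after surgery. Section 7 estimates the difference in means with a 95% confidence interval and adds: "We will also present the associated two-sample t-statistic". If the data are not normal, a Mann-Whitney test replaces it. Neither analysis names a covariate.

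Section 4 (Study Design) describes an online randomisation program working at patient level. No stratification factor appears there or in section 6.

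On surgeons, section 6 says: "The plastic surgeon will be informed of the randomization arm and will proceed with the surgery in the usual fashion". The same sentence goes on to call the procedures standard and equivalent for both, listing aseptic technique, drain placement and antibiotics. It says nothing about when a drain comes out, and neither does the rest of the document. Section 1 notes that "currently at the Ottawa Hospital the product used is dependent on surgeon preference".

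The sample size rests on a 4-day difference (14 against 10) "with a standard deviation of 5", which gives 25 patients per arm. The plan continues: "Allowing for a 10% study drop out rate, we will require a total of 56 pts or 28 patients per arm".

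Sections 4, 7 and 8 enter each breast of a bilateral patient as a separate record, with both breasts in the same arm.

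**The concern.** When a drain is removed is partly a clinical decision. With no written criterion, surgeons may differ in when they make it. If so, differences between surgeons sit in the error term of the two-sample comparison, and an uneven mix of surgeons between arms passes straight into the estimate.

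Two things make this worth attention here. The trial is small, so chance imbalance is common. The sample size also has little to spare, since the planned test has about 79% power at 25 per arm. Surgeon and laterality are both fixed before treatment, so stratifying and adjusting for them is legitimate and needs no new data collection.

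**Working it through.** **Inputs.** From section 7: difference 4 days, SD 5, 25 per arm, dropout 10%. Not stated: significance level and power. I take two-sided 5% and 80%, because these reproduce the plan's figure. Not stated: number of surgeons and the share R of variance due to surgeon. I assume 3 to 5 surgeons (6 in one check) and R from 0 to 30%.

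**1. The plan's sample size.** n per arm = 2 × (1.960 + 0.842)² × 5² / 4² = 2 × 7.849 × 25/16 = 24.5, so 25. Then 50/0.9 = 55.6, so 56. Both figures reproduce. Two-sided 5% with 90% power would give 33 per arm, and one-sided 5% with 80% would give 20.

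**2. Power of the planned test.** SE = 5 × √(2/25) = 1.41 days. Noncentrality = 4/1.41 = 2.83. With 48 degrees of freedom, power is 79.1% (80.7% by the normal approximation).

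**3. Stratified and adjusted.** With surgeon balanced between arms, residual SD = 5√(1 − R) and SE = residual SD × √(2/25). The fourth column uses the noncentral t with 4 surgeons (45 df). The last column is simulation with blocks of 4.

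| R (assumed) | Residual SD | SE (days) | Power, formula | Power, simulated |
|---|---|---|---|---|
| 0% | 5.00 | 1.41 | 79.0% | 78-80% |
| 5% | 4.87 | 1.38 | 81.0% | 81-82% |
| 10% | 4.74 | 1.34 | 83.1% | about 83% |
| 20% | 4.47 | 1.26 | 87.2% | 86-87% |
| 30% | 4.18 | 1.18 | 91.1% | 90-91% |

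**4. Adjusted without stratification.** Simulated power, unadjusted then adjusted, 6,000 trials per cell:

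| R (assumed) | 3 surgeons | 6 surgeons |
|---|---|---|
| 0% | 79.9 → 77.9 | 79.4 → 74.4 |
| 10% | 80.5 → 81.4 | 80.0 → 78.6 |
| 20% | 82.2 → 86.0 | 80.3 → 83.2 |
| 30% | 82.8 → 89.3 | 81.0 → 87.2 |

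Adjustment alone therefore loses about 2 to 5 points when surgeon explains nothing and roughly breaks even at 10%.

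**5. Validity of the planned test.** In the same simulations its type I error was 4.6% to 5.6%, and both estimators centred on the true 4 days.

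**6. Chance imbalance.** With unstratified 25:25 allocation and 3 or 5 surgeons, some surgeon's share of cases differs between arms by at least 20 percentage points about one time in three (roughly 30% to 40%, depending on how caseloads are set). If that surgeon's drains stayed in 4 days longer than colleagues' (an assumption), a 20-point difference would shift the estimate by 0.20 × 4 = 0.8 day, one fifth of the target difference.

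**The case against.** **The premise is not documented.** Nothing in the protocol says surgeons differ in drain duration. A reader might take the remark on surgeon preference in section 1 as evidence that they do. It concerns only the choice of matrix product, which randomisation removes. This stands: a surgeon effect is plausible because no removal criterion is written, but it is neither stated nor measured. Equally, the wording on standard, equivalent procedures in section 6 does not rule it out, since it equates the two arms and mentions drain placement, not removal.

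**The planned analysis is not wrong.** A reader might infer that the unadjusted estimate is biased or its test invalid. Over repeated randomisations it is neither (step 5), and the stated sample size is not in error. This stands in full.

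**The gain may be smaller than it looks.** When surgeon effects are drawn afresh for each simulated trial, a few surgeons show less spread than the nominal share, so total SD falls below 5 and the unadjusted test reaches 80-83%. Within a stratified trial of that kind, adjustment adds about 2-3, 6 and 7-8 points at shares of 10%, 20% and 30%. If total SD is held at the planned 5, the planned unstratified test stays at about 79%, so that comparator is fair for the whole change.

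**There is some slack.** Enrolling 28 per arm gives 83.6% power if nobody drops out, and the endpoint comes early. This stands in part, since the plan counts on only 25 per arm.

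**Laterality is unquantified.** The power figures cover surgeon only. Crossing 3 to 5 surgeons with laterality gives 6 to 10 strata for 56 patients, about 9 to 6 per stratum. This stands and is why laterality is conditional in the fix.

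**Conclusion.** This is a worthwhile low-cost improvement, not an error. The plan neither stratifies nor adjusts for a pre-treatment factor that may influence its primary endpoint, so precision may be lost and a chance imbalance of surgeons would go uncorrected.

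The gain from doing both is about 4, 7 to 8 and 11 to 12 points of power over 79%, at assumed surgeon shares of 10%, 20% and 30%. The most it costs is about 1 point if surgeon explains nothing. These figures rest on 3 to 5 surgeons, total SD 5, 25 per arm, two-sided 5% and one independent value per patient. Neither the surgeon numbers nor the shares come from the documents, so they show a range and do not forecast the gain.

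**What to change.** - **Randomisation.** Set surgeon as a stratification factor in the online program, with low-volume surgeons pooled into one stratum. State which surgeon defines the stratum, since both a breast and a plastic surgeon are involved. Add unilateral/bilateral only if the strata stay adequately filled.
- **Primary analysis.** Prespecify the arm coefficient, with 95% CI, from a linear model of drain days on arm and the stratification factors.
- **Unit of analysis.** Use one drain-duration value per patient, with the rule for bilateral cases written down, or keep breast-level records with standard errors clustered by patient. A laterality term alone does not deal with the correlation between two breasts of one patient.
- **Supporting analyses.** Keep the unadjusted mean difference and the Mann-Whitney test.

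**Cost.** One setting in the program and a few sentences in section 7, plus a few degrees of freedom and some risk of sparse strata.

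**Timing.** Stratification must be set before enrolment, and the model fixed before any data by arm are seen. If enrolment has begun unstratified, the case for making the adjusted model primary is weaker, because of the 2 to 5 point loss when surgeon explains little.

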The significant impact on reduced operative procedures for the patient [6-9], psychological benefit from having restoration of the breast immediately post mastectomy (i.e. direct to implant breast reconstruction) [10-11], cost savings from sparing a second surgery [12-15] as well as improved aesthetic outcomes (compared to non-ADM assisted breast implant reconstruction) [16-17] has made the ADM-assisted approach to become a standard of care at many centers and widely adopted throughout the world [18-21]. Currently at the Ottawa Hospital, a cursory audit in 2015 demonstrated that approximately 50% of the 800 breast cancer patients underwent a mastectomy; 25% of these underwent immediate breast reconstruction for which ADM is used (i.e. around 100 breast cases per year).

Patients who undergo direct-to-implant breast reconstruction with ADMs have been found to experience similar rates of postoperative complications compared with patients who undergo two-stage reconstruction without ADMs, and therefore this procedure is generally considered to be a safe and reliable approach to breast reconstruction [18-23]. A summary of the evidence on outcomes after direct-to-implant breast reconstruction using ADMs is presented in Table 1. Overall, direct-to-implant reconstruction outcomes compare favourably with the Mentor and Allergan Core Study results, which tracked complications and revision rates following delayed two-stage implant reconstruction without ADM (24,25). On short-term follow-up, weighted analysis of the studies in [Table 1](#) shows direct-to-implant reconstruction with ADM to have lower rates of capsular contracture compared to two-stage reconstruction without ADM (0.3% versus 8.3% to 17.1%), seroma (1.2% versus 4.9%), infection (1.4% versus 3.2% to 5.7%), late revision (8.5% versus 27% to 53.3%) and implant loss (1.5% versus 5.7% to 7.7%). Higher rates of mastectomy flap necrosis in immediate reconstruction with ADM (4.7% versus 2.3%) may be

November 24, 2016

related to increased tension placed on the skin closure with immediate placement of the permanent prosthesis.

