## **2. Study Aim**

The aim of this study is to evaluate the postsurgical complications of AlloDerm versus Dermacell use in immediate breast reconstruction.

November 24, 2016

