### **4. Study Design**

In this randomized superiority trial, the site investigator will have the on-line program uploaded to their health authority secured computer in clinic or electronic portable device (e.g. smartphone) in order to randomize participants. The surgeon must dictate that the verbal consent and eligibility review has taken place prior to randomization.

Inclusion Criteria:

- Female patient
- Ages 20-90

November 24, 2016

- All patients undergoing mastectomy for breast cancer or prophylaxis for breast cancer with immediate implant-based reconstruction
- Able to provide verbal consent

Exclusion Criteria:

- Patients who have had prior chest wall or irradiation on the reconstructed side
- Patients not undergoing immediate breast reconstruction at the time of mastectomy
- Any patient with a contraindication to immediate breast reconstruction

It should be noted that patients who undergo bilateral mastectomy and bilateral immediate implant reconstruction should be randomized to the same type of ADM for each breast ie the randomization is at the patient level and not the breast level. Patients having bilateral mastectomy will have each breast evaluated separately, as 2 entries the final results database. Both breasts of the same patient will receive the same randomization arm.

A history of smoking, BMI > 40, and D cup breast size or grade III ptosis are all contraindications to immediate breast reconstruction as the risk of postoperative complications are significantly higher (wound infection, dehiscence, implant loss, seroma) than the average patient and thus these patients would be excluded from the study.

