**Figure 1: Illustration of role of acellular dermal matrix in implant based reconstruction.**

November 24, 2016

**Table 1**Use of acellular dermal matrices in direct-to-implant breast reconstructive surgery

Author (reference), country	Title	Acellular dermal matrix	Sample	Follow-up	Mastectomy flap necrosis requiring revision, %	Capsular contracture rate, %	Late revision rate, %	Seroma rate, %	Infection rate, %	Implant extrusion or requirement for autologous salvage, %
Ashikari et al (24), USA	Subcutaneous mastectomy and immediate reconstruction for prevention of breast cancer for high-risk patients	AlloDerm® a 4 cm × 12 cm	65 patients, 130 breasts One stage	4.6 years ± 5.6 months	N/D	N/D	N/D	N/D	0	N/D
Austen et al (25), USA	A simplified technique for single stage breast reconstruction	AlloDerm® 4 cm × 12 cm 4 cm × 16 cm	25 patients, 35 breasts One stage	10 months	5.7 (2 cases revised in office setting)	N/D	8.6 (1 implant exchanged for asymmetry, one for rippling)	N/D	N/D	2.9
Breuing et al (11), USA	Immediate bilateral breast reconstruction with implants and inferolateral AlloDerm slings	AlloDerm® 4–6 cm × 14–16 cm	10 patients, 20 breasts One stage	6 months to 1 year	5 (Revised in office setting)	0	0	0	0	0
Colwell et al (26), USA	Retrospective review of 331 consecutive immediate single stage implant reconstructions with acellular dermal matrix: Indications, complications, trends and costs	AlloDerm®	211 patients, 331 breasts One stage	N/D	9.1	N/D	N/D	1.5	3.0	1.5
Gamboa-Bobadilla (27), USA	Implant breast reconstruction using acellular dermal matrix	AlloDerm® 4 cm × 16 cm	11 patients, 13 breasts One stage	14 months	N/D	N/D	N/D	7.7	7.7	7.7
Salzberg et al (28), USA	An 8-year experience of direct-to-implant immediate breast reconstruction using human acellular dermal matrix (AlloDerm)	AlloDerm®	260 patients, 466 breasts One stage	28.9±21.3 months	1.1	0.4	9.4 (Most frequent revision was to increase implant size) Both cases (2) required operative intervention	N/D	0.2	1.3
Salzberg et al (29), USA	Nonexpansive immediate breast reconstruction using human acellular tissue matrix graft (AlloDerm)	AlloDerm®	49 patients, 76 breasts One stage	18 months (range 3–52 months)	3.9 (2 managed conservatively with dressings, one managed operatively)	0	N/D	0	0	0

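### Section 7 analyses the dichotomous complications by relative risk alone, and for capsular contracture, seroma and implant loss that statistic will often not exist

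*Combined protocol and SAP*

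**What the plan says.** Section 7 lists the outcomes as "Our dichotomous secondary outcomes (episodes of seroma formation requiring aspiration, loss of implant, revisional surgery/ return to operating room, wound dehiscence or debridement, capsular contracture" and states that they "will be analyzed by calculating relative risk ratios and their 95% confidence intervals". That is the whole analysis for them. The same section gives the drain-duration and clinic-visit outcomes a rank-test alternative if the data do not suit a t-test; the binary outcomes have no alternative.

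The trial is small: "we will require a total of 56 pts or 28 patients per arm", which allows for dropout from 25 evaluable per arm. Section 4 (Study Design) says that "the randomization is at the patient level and not the breast level", but Section 7 has "each breast evaluated separately, as 2 entries the final results database" for bilateral cases. The number of units per arm therefore lies between 25 (evaluable patients, all unilateral) and 56 (28 patients, all bilateral, none lost). Section 5 limits the secondary outcomes to 6 months after surgery. Section 2 gives the aim as to "evaluate the postsurgical complications of AlloDerm versus Dermacell use in immediate breast reconstruction".

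**The concern.** A relative risk needs events. Two cases must be kept apart.

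- **No event in either arm.** The relative risk is 0/0 and does not exist.
- **No event in exactly one arm.** The estimate is zero or infinite and the usual log-scale interval cannot be computed. A score interval still bounds the ratio on one side.

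The protocol's own Table 1 gives rates near or below 1.5% for three of the five outcomes. With a few dozen units per arm, one or other case is then the expected result. The stated analysis would yield nothing, or the analyst would choose a repair after seeing the counts, for outcomes that Section 2 makes the aim of the study.

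**Working it through.** **The plan's own figures.** With a 4-day difference, SD 5, and an assumed two-sided 5% level and 80% power (neither is stated), n per arm = 2 × (1.96 + 0.84)² × 5²/4² = 24.5, so 25 per arm and 50 in total; 50/0.9 = 55.6, so 56. Both match Section 7. The contracture denominator in Table 1 also reproduces: 20 + 466 + 76 + 35 + 30 = 627 breasts, and 0.4% of 466 is 2 events.

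**Inputs.** Rates r are the Table 1 one-stage averages: contracture 2/627, seroma 6/505, implant extrusion or salvage 15/1006, flap necrosis requiring revision 47/993 (nearest row to dehiscence or debridement) and late revision 47/551. Units per arm are n = 25 and n = 56, with n = 47 as an intermediate case. The nine one-stage series in Table 1 (for example "260 patients, 466 breasts") total 1136 breasts in 678 patients, and 28 × 1136/678 = 46.9.

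**Formulas.** With the same r in both arms and independent units, one arm is empty with probability z = (1 − r)^n. Both arms are empty with probability z², and at least one with 1 − (1 − z)². For contracture at n = 25: z = (1 − 2/627)^25 = 0.923, z² = 0.852, and 1 − (0.077)² = 0.994.

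| Outcome | Both arms empty, n = 25 / 47 / 56 | At least one arm empty, n = 25 / 47 / 56 |
|---|---|---|
| Contracture | 85% / 74% / 70% | 99% / 98% / 97% |
| Seroma | 55% / 33% / 26% | 93% / 82% / 76% |
| Implant loss | 47% / 24% / 19% | 90% / 74% / 68% |

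For the other two outcomes at n = 25 and n = 56:

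| Outcome | Both arms empty | At least one arm empty |
|---|---|---|
| Dehiscence (flap-necrosis proxy) | 9% and 0.4% | 51% and 13% |
| Revision | 1% and under 0.1% | 20% and 1% |

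**Sensitivity.**
- *Rate.* The Wilson 95% limits for 2/627 are 0.09% and 1.16%. At the upper limit, contracture is 0/0 with probability (1 − 0.0116)^50 = 56% at 25 per arm and (1 − 0.0116)^112 = 27% at 56. The 0/0 probability falls below 50% once the rate exceeds 1 − 0.5^(1/50) = 1.4% (n = 25) or 1 − 0.5^(1/112) = 0.6% (n = 56).
- *Clustering.* For 28 bilateral patients per arm with within-patient correlation 0.3, a patient is event-free with probability (1 − r)² + 0.3r(1 − r). Raised to the power 28 and squared, this gives 74%, 32% and 24% for the three outcomes, slightly above the independent-breast figures.
- *Two-stage, no-ADM rates.* At the lowest rates in the Background (8.3%, 4.9% and 5.7%) with n = 25, 0/0 has probability 1%, 8% and 5%.

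**What a repair after the fact would do.** For 0/25 against 1/25, a Koopman score interval gives RR 0 with upper limit 3.7. Adding 0.5 to each cell gives (0.5/26)/(1.5/26) = 0.33, with SE of the log √(1/0.5 − 1/26 + 1/1.5 − 1/26) = 1.61 and interval 0.01 to 7.8. Adding 0.5 to 0/25 against 0/25 gives RR 1.0 (0.02 to 48.5) from no events at all.

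**The case against.** The strongest reply is that little turns on this. These are secondary outcomes with no power claim, and the primary outcome is itself treated in Section 1.1 as a measure of seroma formation, so the aim does not rest on these ratios alone. With no events in either arm, any competent report would say so. When only one arm is empty, a score interval already satisfies the wording of Section 7, which does not prescribe the log method. All of this stands, and it limits the consequence. It does not supply a statistic for the 0/0 case or settle the method in advance.

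The rates can also be attacked. The contracture figure rests on two events. All the series used AlloDerm, so equal Dermacell rates are assumed. Table 1's seroma, extrusion or salvage, necrosis and late-revision rows are proxies for the trial's definitions, and follow-up mostly differs from 6 months. This stands too, and the percentages should be read as orders of magnitude. The uncertainty runs both ways: mostly longer follow-up in Table 1 could mean lower 6-month rates. The two-stage rates, at which the problem largely disappears, describe a different procedure without ADM, followed for 3 or 7 years.

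A reader might infer that the analysis fails for all five complications. Table 1 does not support that: at 8.5%, revision would give about 4 to 10 events in the whole trial.

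**Conclusion.** The point holds for three of the five outcomes. At Table 1 rates, 0/0 is more likely than not across the whole range of units only for capsular contracture (85-70%), and even that is not robust to the upper limit of its rate (56-27%). For seroma (55-26%) and implant loss (47-19%) it is common. An empty arm, which defeats the usual log-scale interval, is the expected result for all three. The figures assume literature AlloDerm rates, equal rates in both arms and independent units.

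It would be tempting to conclude that the trial's findings are at risk. They are not: the primary analysis and sample size are unaffected, and at the likely counts every repair gives an interval that includes 1. What changes is the reported estimate and its width, and whether the method was fixed beforehand. The change should be made before analysis, but the trial does not depend on it.

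**What to change.** Add to Section 7:

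> For each dichotomous outcome we will report the number of patients with at least one event by arm and the risk difference with a Newcombe 95% confidence interval, which is the governing result. The relative risk with a Koopman score-based 95% confidence interval will be supplementary, and will be reported as not estimable if neither arm has an event.

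The counts are on patients because patients are randomised. If breasts remain the unit, the interval must allow for within-patient clustering, since the standard Newcombe and Koopman intervals assume independent units.

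One interval has to govern because the two can disagree: for 0/25 against 4/25 the Newcombe upper limit is +0.4 percentage points (includes no difference) and the Koopman upper limit is 0.89 (excludes 1). At the Table 1 rates a split of 0 against 4 or more has a probability of at most 4% for any of the five outcomes.

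The cost is wording and a little analysis. Patient-level counts come from the breast entries already planned. There are two downsides. Intervals stay wide: 0/25 against 0/25 gives about ±13 points and 0/25 against 1/25 gives −4 (−20 to +10), so these outcomes support only limited conclusions. And the summary becomes the risk of any event per patient, not the risk per breast.

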## **8. Data Collection**

Once the patient has been randomized, the study CRA will collect participant information via electronic health records. From a study standpoint only the CRA will access this information. Data not available at the time of visit will be collected from the dictated physician/surgeon note. At the time of randomization the software will also generate a reminder email to the patient's physician to collect study related data. Patients having bilateral mastectomy will have each breast evaluated separately, as 2 entries the final results database. However, both breasts of the same patient will receive the same randomization arm.

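### The trial randomises and counts patients but enters each bilateral patient as two same-arm records with no method for pairing, so the primary test and 95% CI are too optimistic

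*Combined protocol and SAP*

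**What the plan says.** Section 4 (Study Design) is explicit about the unit of allocation: "the randomization is at the patient level and not the breast level". Section 7 sizes the trial in the same unit: "we will require 50 patients total (25 per arm) to demonstrate a 4 day difference in drainage duration", which becomes 56 patients after a 10% allowance for dropout.

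The analysis paragraph of Section 7 compares mean drain duration with a 95% CI and adds "We will also present the associated two-sample t-statistic". The fallback is "If data are not normally distributed, we will compare groups using a Mann-Whitney test". Dichotomous secondary outcomes get relative risks with 95% CIs, and extra clinic visits get a t or Mann-Whitney test. The same paragraph ends with the rule "Patients having bilateral mastectomy will have each breast evaluated separately, as 2 entries the final results database". Section 4 (Study Design) and Section 8 repeat that rule, and Section 8 adds "However, both breasts of the same patient will receive the same randomization arm".

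Neither the protocol nor the analysis plan mentions within-patient correlation, a patient-level summary, an index breast, a mixed model, GEE or a cluster-robust standard error.

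**The concern.** A bilateral patient is a cluster of two lying wholly within one arm. Her breasts share the patient, the allocated matrix and the operation, so their drain durations should be positively correlated. Two such records carry less information than two unrelated patients, but the named tests give them full weight.

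At stake is the primary result of a small superiority trial. If the tests are run on the database rows, the CI for the difference is too narrow and the test rejects too often. The design counts patients while the analysis counts breasts: at an assumed 20% to 68% bilateral, 50 patients yield 60 to 84 records.

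Extra clinic visits raise a sharper form of the problem. They are counted per patient, and the plan does not say how they are entered for a patient with two rows. If the count is copied into both rows, the within-patient correlation is 1.

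**Working it through.** **1. The plan's own sample size.** Inputs from Section 7: difference 4 days, SD 5. Alpha and power are not stated; two-sided 5% and 80% are assumed. n per arm = 2 × (1.960 + 0.842)² × 5² / 4² = 24.5, rounded up to 25, so 50 in total. 50 / 0.9 = 55.6, rounded up to 56. Both figures reproduce, and both count patients. Exact t power at 25 per arm is 79.1%.

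**2. Inputs the documents do not give.**
- *Bilateral share p.* Assumed 20% to 68%. The upper value comes from Table 1: 678 patients, 1136 breasts, 1136 / 678 − 1 = 0.676. Leaving out the prevention series and the series that is bilateral by title gives 986 / 603 − 1 = 0.64. These are other centres' patients. The local audit figure in Section 1, "around 100 breast cases per year", does not establish a share.
- *Within-patient correlation (ICC).* Assumed 0.3 to 0.8.

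**3. Variance inflation.** An arm of n patients has m = n(1 + p) records and np pairs. The variance of its mean is (σ²/m) × DEFF, with

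DEFF = 1 + [2p / (1 + p)] × ICC.

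This exceeds 1 for any ICC above 0 once one bilateral patient is enrolled. The actual error of a nominal 5% test is about 2 × [1 − Φ(1.96 / √DEFF)], and the CI is too narrow by 1 − 1/√DEFF. For p = 0.3 and ICC 0.5: DEFF = 1 + (0.6 / 1.3) × 0.5 = 1.231, 1.96 / √1.231 = 1.767, error 7.7%.

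**4. Results for the primary t-test on breast records, 25 patients per arm** (simulation: 40,000 null trials per row)

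| Bilateral | ICC | DEFF | Type I error, formula | Type I error, simulated | CI too narrow by |
|---|---|---|---|---|---|
| 20% | 0.3 | 1.100 | 6.2% | 5.9% | 4.7% |
| 30% | 0.5 | 1.231 | 7.7% | 7.7% | 9.9% |
| 30% | 0.8 | 1.369 | 9.4% | 9.3% | 14.5% |
| 68% | 0.8 | 1.645 | 12.7% | 12.8% | 22.0% |

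Simulated coverage of the 95% CI runs from 94.1% (first row) to 87.2% (last row). Repeat simulations moved the error rates by no more than about half a percentage point.

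**5. Other outcomes.**
- *Mann-Whitney on breasts* (6,000 trials, whole days): 5.7% in the first-row setting, 12.1% in the last.
- *Clinic visits, if duplicated (ICC 1):* DEFF = 1 + 0.4 / 1.2 = 1.333 at 20% bilateral, error 9.0%; at 68% the error is 14.5%.
- *Relative risks:* no general inflation. At an assumed 20% risk per breast the log-Wald test on breasts has an error of 3.3% to 9.9%. At 10% risk it is 0.5% to 4.0%, because events are few.

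**6. One value per patient.** With the mean of two breasts for bilateral patients, the ordinary t-test had a simulated error of 4.7% to 5.1% across the grid, and Mann-Whitney 5.0% and 4.8% in the two settings above.

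**The case against.** The strongest reply is that the two-entries sentence is a data-entry rule. It speaks of evaluation and a database, it recurs in the Study Design and Data Collection sections, and no sentence says that the t-test runs on breast rows. That is true, and the independence assumption is inferred from how the named tests are ordinarily computed. But in Section 7 the sentence closes the analysis paragraph, and no step turns two rows into one. Even on the kinder reading, the unit of analysis for the primary endpoint is undefined.

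Second, the size is not anchored in this trial. The top figures need both a 68% bilateral share taken from other centres and an ICC of 0.8; at 20% and 0.3 the error is only about 6%. This stands. The direction is certain for positive correlation, but the magnitude is conditional.

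Third, Table 1's weighted complication rates are 0.3% to 8.5%, so the relative-risk inflation seen at 20% risk is not shown at the documents' own rates. This also stands, and the point rests on drain duration and clinic visits.

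Fourth, other repairs are valid, and counting a patient as affected if either breast is affected changes the quantity from risk per breast to risk per patient. That is fair. It concerns the secondary outcomes and can be decided separately.

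**Conclusion.** The concern holds. Followed as written, the plan gives a primary 95% CI that is too narrow and a test that rejects too often, for any positive within-patient correlation and at least one bilateral patient. Under the assumed ranges (20% to 68% bilateral, ICC 0.3 to 0.8, two-sided 5%, 25 patients per arm) the effect runs from minor to more than double the nominal error. The patient-based sample size is not at fault; the defect lies in the analysis. It should be settled before the data are analysed, so that the unit is not chosen with results in view.

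**What to change.** Replace the two-entries sentence in Section 7 with wording such as: *Each breast is recorded separately, but the patient is the unit of analysis. For drain duration, a bilateral patient contributes the mean of her two breasts. Additional clinic visits are entered once per patient. For each dichotomous outcome, a patient is counted once, as affected if either breast is affected. The numbers 50 and 56 count patients.* Align the matching sentences in Section 4 (Study Design) and Section 8.

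The mean difference, 95% CI and t-test, or Mann-Whitney if needed, are then computed on one value per patient. As a sensitivity analysis, add a breast-level mixed model with a patient random intercept and a small-sample degrees-of-freedom correction. Breast-level complication rates can be reported descriptively. If the team prefers risk per breast for the dichotomous outcomes, the plan should say so and name a method that allows for the pairing.

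The cost is wording and wider intervals, with no extra patients. The average CI half-width goes from 2.57 to 2.73 days (20% bilateral, ICC 0.3) or from 2.15 to 2.73 days (68%, ICC 0.8). With 25 per arm, power for 4 days is about 80% to 89% if SD 5 describes a single breast, and 79.1% if it describes a patient-level value. Section 7 should state which it is, along with alpha and power.
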